20.4.2 BAX 855 Naïve Subjects on Fixed Dose Prophylactic Treatment Regimen

Assessments ^a	Screening Visit ^b	ED1 (Baseline)	Follow-Up Visits		End of Study Visit ^c
			6 ± 1 Week Following Baseline	Every 3 Months ± 2 Weeks Following Baseline ^d	
FVIII tests ^d	P				
FVIII pre-infusion		P	P	P	P
FVIII post-infusion		P	P	P	P
TGA pre-infusion (optional)		P	P	P	P
TGA post-infusion (optional)		P	P	P	P
VWF antigen (pre-infusion) (optional)		P	P	P	P
Immunogenicity assays ^e	P	P	P	P	P
Hematology ^f	W		W	W	W
CD4 count	W			W ^g	
Blood type ^h	W				
Genetics and HLA-genotype	P				
Clinical chemistry ⁱ	S		S	S	S
Lipid panel ^j	S		S	S	S
Viral serology ^k	S				

Abbreviations: W = whole blood; P = plasma; S = serum.

^a At all visits subjects must not be actively bleeding and a washout period of at least 84 to preferably 96 hours following the previous dose of BAX 855 or at least 72 hours following the previous dose of another FVIII concentrate should be observed for blood sampling. All laboratory tests will be performed at a central laboratory.

^b Laboratory assessments are to be completed within 45 days prior to the first infusion of BAX 855.

^c Including cases of withdrawal or discontinuation.

^d FVIII tests are: 1-stage clotting FVIII activity, FVIII chromogenic activity, and FVIII antigen. Samples will be taken within 30 minutes before and 30 ± 15 minutes after infusion of 60 ± 5 IU/kg of BAX 855.

Continued on Next Page

Continued

- ^e Immunogenicity assays are: inhibitory antibodies to FVIII, binding antibodies to FVIII, BAX 855 and PEG, anti-CHO antibodies. For binding antibodies, both IgG and IgM antibodies will be measured.
- ^f Hematology includes: hemoglobin, hematocrit, red blood cell count, white blood cell count with differential (ie, basophils, eosinophils, lymphocytes, monocytes, and neutrophils), mean corpuscular volume (MCV), mean corpuscular hemoglobin concentration (MCHC), platelet count.
- ^g CD4 count to be tested every 6 months in subjects who are HIV positive.
- ^h If historical data on blood group type is available, this may be recorded in the eCRF and blood type does not need to be measured.
- ⁱ Clinical chemistry includes: Sodium, potassium, chloride, bicarbonate, total protein, albumin, ALT, AST, total bilirubin, alkaline phosphatase, BUN, creatinine, and glucose.
- ^j Lipid panel includes: cholesterol, VLDL, LDL, HDL, and triglycerides.
- ^k Viral serology includes: HIV-1Ab, HIV-2 Ab, HBcAb, HBsAb, HBsAg, and HCVAb. Any positive viral antibody test will be repeated using a new blood sample in case the positivity is not part of the medical history. Any HIV or HCV positive sample will be tested by PCR for viral titer.

20.4.3 Subjects on PK-Tailored Prophylactic Treatment Regimen (Transitioning and BAX 855 Naïve Subjects)

Assessments ^a	Screening Visit ^{b,c}	PK Assessment ^d	Baseline/ Start of Prophylaxis 6 ± 1 Weeks ^e	Follow-Up Visits		End of Study Visit ^g
				4 ± 1, 8 ± 1, 18 ± 2 Weeks Following Baseline ^f	Every 3 Months ± 2 Weeks Following Baseline	
FVIII tests ^h	P (N)					
FVIII pre-infusion	P (T*)	P	P	P	P	P
FVIII post-infusion	P (T*)	P	P		P	P
TGA pre-infusion ⁱ		P	P	P	P	P
TGA post-infusion ⁱ		P	P		P	P
VWF antigen (pre-infusion) ⁱ		P	P	P	P	P
Immunogenicity assays ^j	P (T* / N)	P (N)	P		P	P
Hematology ^k	W (T* / N)		W		W	W
CD4 count	W				W ^l	
Blood type ^m	W (N)					
Genetics and HLA-genotype	P (N)					
Clinical chemistry ⁿ	S (T* / N)		S		S	S
Lipid panel ^o	S (T* / N)		S		S	S
Viral serology ^p	S					

Abbreviations: W = whole blood; P = plasma; S = serum. T = transitioning subjects (* denotes that data are transcribed from end of study visit of the previous BAX 855 study for transitioning subjects. However, for subjects transitioning from the surgery study (Study 261204), FVIII assays and lipid panel are not part of the end of study assessments of the previous BAX 855 study and must be performed at screening); N = BAX855 naïve subjects.

^a At all visits subjects must not be actively bleeding and a washout period of at least 84 to preferably 96 hours following the previous dose of BAX 855 or at least 72 hours following the previous dose of another FVIII concentrate should be observed for blood sampling. All laboratory tests will be performed at a central laboratory.

^b Laboratory assessments are to be completed within 45 days prior to the first infusion of BAX 855 for BAX855 naïve subjects.

^c For subjects transitioning from the pivotal study (Study 261201), there is an optional assessment of IR at screening (in some BAX 855 studies, IR is assessed at the end of study visit and the results can be transcribed).

Continued on Next Page

Continued

- ^d PK assessment does not need to be performed in transitioning subjects who have already undergone a PK assessment in a previous BAX 855 study. For these subjects the baseline/start of prophylaxis visit will be the first visit after screening and eligibility will be confirmed at this visit. PK assessment for subjects aged ≥ 12 years: Pre- and post-infusion blood draws over a period of 96 hours following the infusion of 60 ± 5 IU/kg of BAX 855 within 30 minutes before infusion and 0.25, 3, 9, 32, 56, and 96 hours post-infusion; PK assessment for subjects aged < 12 years: Pre- and post-infusion blood draws over a period of 56 hours following the infusion of 60 ± 5 IU/kg of BAX 855 within 30 minutes before infusion and 0.25, 9, and 56 hours post-infusion.
- ^e Baseline/start of PK-tailored prophylaxis starts 6 ± 1 weeks following either PK determination in case the patient has not undergone a PK assessment in a previous BAX855 study, or 6 ± 1 weeks following screening if a PK assessment is already available (this visit will then coincide with confirmation of eligibility).
- ^f Only FVIII trough levels and TGA parameters (subjects ≥ 12 years) prior to the next prophylactic infusions are to be performed to determine whether the subjects remains at FVIII trough levels of a minimum of 3%.
- ^g Including cases of withdrawal or discontinuation.
- ^h FVIII tests are: 1-stage clotting FVIII activity, FVIII chromogenic activity, and FVIII antigen. Samples will be taken within 30 minutes before and 30 ± 15 minutes after infusion of 60 ± 5 IU/kg of BAX 855.
- ⁱ The assessment of TGA parameters and determination of pre-infusion VWF antigen level are optional in subjects aged < 12 years.
- ^j Immunogenicity assays are: inhibitory antibodies to FVIII, binding antibodies to FVIII, BAX 855 and PEG, anti-CHO antibodies. For binding antibodies, both IgG and IgM antibodies will be measured.
- ^k Hematology includes: hemoglobin, hematocrit, red blood cell count, white blood cell count with differential (ie, basophils, eosinophils, lymphocytes, monocytes, and neutrophils), mean corpuscular volume (MCV), mean corpuscular hemoglobin concentration (MCHC), platelet count.
- ^l CD4 count to be tested every 6 months in subjects who are HIV positive.
- ^m If historical data on blood group type is available for BAX 855 naïve subjects, this may be recorded in the eCRF and blood type does not need to be measured.
- ⁿ Clinical chemistry includes: Sodium, potassium, chloride, bicarbonate, total protein, albumin, ALT, AST, total bilirubin, alkaline phosphatase, BUN, creatinine, and glucose.
- ^o Lipid panel includes: cholesterol, VLDL, LDL, HDL, and triglycerides.
- ^p Viral serology includes: HIV-1Ab, HIV-2 Ab, HBcAb, HBsAb, HBsAg, and HCVAb. For BAX 855 naïve subjects, any positive viral antibody test will be repeated using a new blood sample in case the positivity is not part of the medical history. Any HCV positive sample will be tested by PCR for viral titer.

20.5 Karnofsky and Lansky Scores

Karnofsky and Lansky Scores for Performance Status		
	Karnofsky Score (Subjects Aged ≥ 16 Years)	Lansky Score (Subjects Aged < 16 Years)
Score	Definition	Definition
100	Normal, no complaints; no evidence of disease	Fully active, normal
90	Able to perform normal activity; minor signs or symptoms of disease	Minor restriction in physically strenuous play
80	Able to perform normal activity with effort; some signs or symptoms of disease	Active, but tires more quickly
70	Cares for self, unable to perform normal activity or to do active work	Both greater restrictions of, and less time spent in active play
60	Requires occasional assistance but is able to care for most of own needs	Up and around, but minimal active play; keeps busy with quieter activities
50	Requires considerable assistance and frequent medical care	Gets dressed, but lies around much of the day; no active play; able to participate in all quiet play and activities
40	Disabled; requires special care and assistance	Mostly in bed; participates in quiet activities
30	Severely disabled; hospitalization indicated, although death not imminent	In bed; needs assistance even for quiet play
20	Very sick; hospitalization necessary; active supportive treatment required	Often sleeping; play entirely limited to very passive activities
10	Moribund; Fatal processes progressing rapidly	No play; does not get out of bed
0	Dead	Unresponsive

Source: Karnofsky et al.¹⁵ and Lansky et al.¹⁶

#### 1. INTRODUCTION AND OBJECTIVES

This document describes the rules and conventions to be used in the planned presentation and analysis of efficacy and safety data for Protocol 261302 as set out in the latest version of the Output Templates. It describes the data to be summarized and analyzed, including specifics of the statistical analyses to be performed.

The purpose of this study is to continue the evaluation of the safety and efficacy of BAX 855 for prophylaxis and treatment of bleeding episodes in adult and pediatric previously treated patients (PTPs) aged  $\leq 75$  years with severe hemophilia A. In the Russian Federation, safety and efficacy are only to be assessed in adults aged  $\geq 18$  and  $\leq 75$  years at the time of enrollment.

## 1.1 Study Objectives

## 1.1.1 Primary Objectives

The co-primary objectives of the study are:

- 1. To determine the safety of BAX 855 based on the incidence of factor VIII (FVIII) inhibitory antibody development.
- 2. To determine the efficacy of BAX 855 based on annualized bleeding rate (ABR) of spontaneous bleeding episodes.

## 1.1.2 Secondary Objectives

## **1.1.2.1** Efficacy

- 1. To determine the total ABR (spontaneous and traumatic bleeding episodes).
- 2. To determine the overall hemostatic efficacy rating of BAX 855 for treatment of breakthrough bleeding episodes.
- 3. To determine the length of intervals between bleeding episodes.
- 4. To characterize the hemostatic efficacy of BAX 855 for treatment of bleeding episodes by number of BAX 855 infusions for treatment.
- 5. To determine total weight-adjusted consumption of BAX 855 for prophylaxis and for treatment of bleeding episodes.

6. To assess Patient Reported Outcomes (PROs) over time for subjects receiving BAX 855.

## **1.1.2.2** Safety

- 1. To determine the safety of BAX 855, as assessed by the occurrence of adverse events (AEs) and changes in vital signs and clinical laboratory parameters.
- 2. To determine the immunogenicity of BAX 855.

## 1.1.3 Exploratory Objectives

- 1. To assess patient satisfaction, patient activity levels, and health resource use over time for subjects receiving BAX 855.
- 2. To determine the potential correlation between thrombin generation assay (TGA) parameters, FVIII trough levels and ABR.

#### 2. STUDY DESIGN

This is a phase 3b, prospective, open label, multi-center study to evaluate the safety and efficacy of BAX 855 for prophylactic use and the control of bleeding episodes in approximately 200 pediatric and adult PTPs  $\leq$  75 years of age with severe hemophilia A. In the Russian Federation, safety and efficacy are only to be assessed in adults aged  $\geq$  18 and < 75 years at the time of enrollment. The study plans to include subjects from other BAX 855 studies and BAX 855-naïve subjects.

Subjects are to receive either a fixed dose prophylaxis with BAX 855 consisting of  $45 \pm 5$  IU/kg for subjects aged  $\geq 12$  years or  $50 \pm 10$  IU/kg for subjects aged  $\leq 12$  years (in all countries except the Russian Federation) twice weekly or, subjects can decide to receive a pharmacokinetic (PK)-tailored prophylactic BAX 855 dosing regimen based on the subject's individual PK to maintain FVIII trough levels of  $\geq 3\%$ . Other treatment regimens were allowed prior to protocol amendment four.

Subjects are to be treated on the specified prophylactic treatment regimen until they reach at least 100 exposure days (EDs) (as accumulated across all BAX 855 studies).

It is to be noted that the use of any FVIII concentrate other than BAX 855 during the course of the study following the first BAX 855 infusion is not permitted. The use of (commercial) ADVATE may be permitted for a short period of time for administrative reasons. It is also to be noted that ADVATE was allowed as rescue medication in

previous versions (prior to amenmdent four) of the protocol for this study under which a number of subjects have been enrolled.

#### 2.1 Inclusion Criteria

Refer to Section 9.1 of the Clinical Study Protocol for information on inclusion criteria.

#### 2.2 Exclusion Criteria

Refer to Section 9.2 of the Clinical Study Protocol for information on exclusion criteria.

#### 2.3 Sample Size and Power Calculations

In total, approximately 250 subjects are to be enrolled in this study. The sample size is based on having 200 evaluable subjects with a minimum of 100 EDs to BAX 855 in accordance with the guidance EMA/CHMP/BPWP/144533/2009.

## 2.4 Randomization and Blinding

This is a non-randomized, open-label, active treatment clinical study.

## 2.5 Study Stopping Rules

Refer to Section 8.6 of the Clinical Study Protocol for information on study stopping rules.

#### 2.6 Study Assessments

Refer to Section 20.3 of the Clinical Study Protocol for a schedule of study procedures and assessments.

#### 2.7 Data Monitoring Committee

A Data Monitoring Committee (DMC) is not to be used for this study as the expected related AEs in this study are anticipated to be similar to that of the licensed product ADVATE (of which the core protein is identical to that of BAX 855). Additionally, the safety is not expected to differ from the safety observed in the BAX 855 pivotal and pediatric studies (Studies 261201 and 261202, respectively).

#### 3. STUDY OUTCOME MEASURES

#### 3.1.1 Primary Outcome Measures

## **3.1.1.1** Safety

1. Development of inhibitory antibodies to FVIII.

## **3.1.1.2 Efficacy**

1. Spontaneous ABR.

#### 3.1.2 Secondary Outcome Measures

#### **3.1.2.1** Efficacy

- 1. Total ABR (spontaneous and traumatic bleeding episodes).
- 2. Overall hemostatic efficacy rating of BAX 855 for treatment of breakthrough bleeding episodes.
- 3. Number of BAX 855 infusions to treat bleeding episodes.
- 4. Time intervals between bleeding episodes.
- 5. Weight-adjusted consumption of BAX 855.

#### 3.1.2.2 Safety

- 1. Occurrence of AEs and serious AEs (SAEs).
- 2. Changes in vital signs and clinical laboratory parameters (hematology, clinical chemistry, and lipids).
- 3. Immunogenicity
  - a. Binding antibodies [immunoglobulin (Ig) G (IgG) and IgM] to FVIII, polyethylene glycol (PEG)-FVIII, and PEG.
  - b. Anti-Chinese hamster ovary (CHO) antibodies.

#### 3.1.2.3 Patient Reported Outcomes

Changes from baseline in parent study, if applicable, in the following:

- 1. Bleed and pain severity as measured using the haemophilia symptoms (Haemo-SYM) questionnaire.
- 2. Health related quality of life (HRQoL) as assessed using the short form-36 (SF-36)/Pediatrics Quality of Life (PedsQL) questionnaires.

#### 3.1.3 Exploratory Outcomes Measure

- 1. Patient satisfaction with treatment is to be assessed using the Satisfaction Question Set.
- 2. Patient Activity Level.
- 3. Health resource use data (e.g., physician office visits, hospitalizations, days missed from work/school).
- 4. TGA parameters, FVIII trough levels and ABR.

#### 4. ANALYSIS SETS

## 4.1 All Subjects Enrolled Set (ENR)

The all subjects enrolled set (ENR) is to contain all subjects that signed informed consent.

Information on whether a subject signed informed consent is to be obtained from the *Informed Consent* electronic case report form (eCRF) panel.

## 4.2 Safety Analysis Set (SAS)

The safety analysis set (SAS) is to comprise all subjects in the ENR with at least one BAX 855 infusion. All safety analyses are to be performed on the SAS.

Information on dosing with BAX 855 is to be obtained from the following eCRF panels:

- Study Infusion eCRF panels.
- *Infusion for Determination of Incremental Recovery* eCRF panels.
- Infusion for PK Assessment eCRF panels.
- *Minor Surgery* eCRF panels.

#### 4.3 Full Analysis Set (FAS)

The full analysis set (FAS) is to comprise of all subjects in the SAS.

#### 4.4 Per Protocol Analysis Set (PPAS)

The per protocol (PPAS) analysis set is to comprise all subjects in the FAS who had no major deviations from the protocol affecting the study results. Protocol deviations are to be obtained from the Clinical Trial Management System (CTMS).

Prior to performing any analysis as set out in this SAP, a meeting is to be held discussing the impact of any major protocol deviation on the analysis. At this meeting, the decision is to be made on whether a subject is to be excluded from the PPAS analysis set or not. The meeting is to be attended by participants from at least Biostatistics and Medical.

Below is a list of possible major deviations that may influence the study results that will be discussed at the analysis set assignment meeting:

- Subject less than 75% exposed to BAX 855 as derived in Section 6.8: Measurements of Treatment Compliance.
- Subject less than 75% compliant to planned dosing regimen.
- More than 10% of treated bleeds have no efficacy rating.
- Use of expired IP.
- Subject did not reach 100 EDs across all BAX 855 studies.
- Use of any FVIII product other than ADVATE, as determined by the medical team.

It should be noted that the above will not necessarily lead to immediate exclusion from the PPAS, but will be discussed prior to locking the database. The database is not allowed to be locked until final approval on the PPAS has been obtained.

During the course of the study, data review meetings are to be held on a regular basis. During these meetings the quality of the data including any potential protocol deviations are to be identified. All protocol deviations identified at these meetings are to be included into the CTMS upon team agreement.

#### 4.5 Pharmacokinetic Analysis Set (PKAS)

The PK analysis set (PKAS) is to comprise of all subjects in the SAS with at least one PK assessment performed in the current study.

#### 5. STATISTICAL CONSIDERATIONS

#### 5.1 Interim Analyses

A first interim safety review is to be performed for license submission to the European Medicines Agency (EMA).

If applicable, a second interim safety review may be performed once 200 subjects have accumulated at least 100 EDs to BAX 855.

#### 5.2 Final Analysis

The final planned analysis identified in this SAP is to be performed by IQVIA Biostatistics following Baxalta's authorization of this SAP and Database Lock.

The final analysis is to be performed on a clean database:

- All outstanding data issues and queries resolved.
- All irresolvable data issues documented in the Data Handling Report (DHR) from Data Management.
- All coding of medications and AEs completed.
- SAE reconciliation completed.
- All reconciliation of vendor data with eCRF data completed successfully.
- Analysis sets authorized.

It is to be noted that all verbatim text from the eCRF to be presented in any outputs are to be presented "as is" with no "manual hard coding" corrections for such data.

## 5.3 Reference Start Date and Study Day

Reference start date is defined as the day of the subject's first BAX 855 infusion in the 261302 protocol (henceforth referred to as the current study) and is to be referred to as Day 1. Subjects that discontinue study participation prior to receiving any BAX 855 dose in the current study will not have a reference start date.

Study Day is to be calculated as described below from the reference start date (first BAX 855 infusion in the current study), and is to be used to show start and stop day of assessments and events.

• If the date of the event is on or after the reference date then:

$$Study Day = (Date of Event - Reference Date) + 1$$

• If the date of the event is prior to the reference date then:

Study Day = (Date of Event - Reference Date)

In the situation where the assessment/event date is partial or missing, study day and corresponding durations are not to be calculated.

#### 5.4 Handling of Missing, Unused, and Spurious Data

Except for the below specified, missing data is not to be imputed.

## **Exposure:**

Should body weight (as obtained from the *Vital Signs* eCRF panels) be missing for a subject at the time of study infusion, the latest available body weight measurement at the time of the infusion is to be carried forward in order to compute body weight-adjusted BAX 855 consumption.

#### **Adverse Events:**

- Handling of unknown causality assessment:
  - o If a subject experiences an AE with a missing causality assessment, the relationship of the AE is to be considered as "related".
- Handling of unknown severity grades:
  - O If a subject experiences more than one AE categorized under the same preferred term, one of them is categorized as "severe" and one of them is categorized as "unknown", then the severity of the AE is to be counted as "severe".
  - o If a subject experiences more than one AE categorized under the same preferred term, one of them is categorized as "mild" or "moderate" and one of them is categorized as "unknown", then the severity of the AE is to be counted as "unknown".

#### **Laboratory Data:**

Imputation of below limit of quantification (BLQ) and above limit of quantification (ALQ) results are described in the applicable analysis sections.

#### 5.5 Definition of Baseline

Except for quality of life analyses, baseline is defined as the last non-missing (scheduled or unscheduled) measurement obtained prior to the reference start date discussed in Section 5.3: Reference Start Date and Study Day. If the date of the last non-missing assessment and the reference start date coincide, the assessment is to be considered baseline. Baseline for quality of life analyses is defined in Section 9: EVALUATION OF PATIENT REPORTED OUTCOMES.

For subjects transitioning to the Continuation study from another BAX 855 study where no result prior to first administration of BAX 855 in the current study is available, the last possible results from the study transitioned from will be used as baseline. The exception would be for height where the Screening result from the predecessor study will be used.

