- FVIII : FVIII activity (1-stage clotting assay and chromogenic assay) and FVIII antigen
- Vital signs (body temperature, respiratory rate, pulse rate, and supine systolic and diastolic blood pressure)

Other procedures:

- Dispense IP:
 - A sufficient quantity of IP will be dispensed to cover the period until the next scheduled visit in 6 ± 1 weeks.

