 - Immunogenicity tests:
 - Inhibitory antibodies to FVIII (Nijmegen assay)
 - Binding antibodies (IgG and IgM) to FVIII, BAX 855, and PEG
 - Anti-CHO antibodies
 - Hematology, clinical chemistry, and lipid panel
- Pregnancy test if female of childbearing potential
- Assessment of inclusion/exclusion criteria
- Provide a subject e-diary and give instructions on use

20.2.1.2 ED1 (Baseline):

Only Applicable to BAX 855 Naïve Subjects

At least 72 hours must have elapsed since the previous administration of any FVIII concentrate, and the subject must not be actively bleeding.

The following procedures will be performed:

Pre-infusion:

- Confirmation of eligibility
- Physical examination, including height (for subjects aged < 18 years at enrollment) and body weight
- Review and discuss subject e-diary, including:
 - Review bleeding episodes and their treatment
 - Adverse events
 - Concomitant medications and non-drug therapies

- Laboratory assessments within 30 minutes of start of infusion:
 - FVIII activity and antigen
 - Immunogenicity tests
 - VWF antigen (optional)
 - TGA parameters (optional)
- PROs:
 - Bleed and pain severity using Haemo-SYM (≥ 18 years), HRQoL using SF-36 (≥ 14 years), HRQoL using PedsQL (< 14 years), patient satisfaction with treatment using the Satisfaction Questionnaire (all ages), and Patient Activity Level (all ages)
- Vital signs (within 15 minutes of start of infusion)

Determination of IR:

- Infusion of 60 ± 5 IU/kg BAX 855

Post-infusion:

At 30 ± 15 min post-infusion:

- FVIII activity and antigen
- TGA parameters (optional)
- Vital signs

Other procedures:

- Dispense IP:
 - A sufficient quantity of IP will be dispensed to cover the period until the next scheduled visit in 6 ± 1 weeks.

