20.2.2.2 PK Assessment

For BAX 855 naïve subjects and transitioning subjects with no prior PK assessment

Blood sampling after infusion of BAX 855 for PK assessments will be performed over a 4-day period for subjects aged ≥ 12 years or a 2.5 day period for subjects aged < 12 years. A minimum wash-out period of 84 to preferably 96 hours prior to the PK infusion is required for subjects transitioning from another BAX 855 study and 72 hours prior to PK infusion for BAX 855 naïve subjects on treatment with any other FVIII concentrate, and the subject must not be actively bleeding.

The following assessments will be performed:

Pre-infusion

- Confirmation of eligibility
- Physical examination, including height (for subjects aged < 18 years at enrollment) and body weight
- Review and discuss subject e-diary, including:
 - Review bleeding episodes and their treatment
 - Adverse events
 - Concomitant medications and non-drug therapies
- Laboratory assessments within 30 minutes of start of infusion:
 - FVIII activity and antigen
 - Immunogenicity tests (BAX855 naïve subjects only)
 - TGA parameters and VWF antigen (optional in subjects aged < 12 years)
- Vital signs (within 15 minutes of start of infusion)

Infusion for PK assessment:

- Infusion of 60 ± 5 IU/kg BAX 855

Post-infusion:

- Laboratory assessments in subjects aged ≥ 12 years:
 - FVIII activity, FVIII antigen and TGA parameters at the following post-infusion time points: 15 min \pm 5 min, 3 h \pm 30 min, 9 h \pm 30 min, 32 h \pm 2 h, 56 h \pm 4 h, and 96 h \pm 4 h
- Laboratory assessments in subjects aged < 12 years:
 - FVIII activity and antigen at the following post-infusion time points: 15 min \pm 5 min, 9 h \pm 30 min, 56 h \pm 4 h
 - Optional TGA parameters at the same timepoints
- Vital signs at 30 min \pm 5 min post-infusion

Other procedures:

- Dispense IP to transitioning subjects:
 - A sufficient quantity of IP will be dispensed to cover the period until the next scheduled visit in 6 ± 1 weeks.

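### SAP 5.5 fixes baseline by date only, so read literally it takes a post-infusion vital sign as the baseline for change

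*SAP*

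**What the plan says.** **Baseline rule.** SAP 5.3 states: "Reference start date is defined as the day of the subject's first BAX 855 infusion in the 261302 protocol". This is a date without a clock time. SAP 5.5 says that, quality of life apart, "baseline is defined as the last non-missing (scheduled or unscheduled) measurement obtained prior to the reference start date". It then adds: "If the date of the last non-missing assessment and the reference start date coincide, the assessment is to be considered baseline". A further paragraph lets a transitioning subject take the last result of the predecessor study "where no result prior to first administration of BAX 855 in the current study is available".

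**Day 1 measurements.**
- BAX 855 naïve, fixed dose (Protocol 20.2.1.2, ED1): the pre-infusion list has "Vital signs (within 15 minutes of start of infusion". Vital signs appear again under the heading "At 30 ± 15 min post-infusion".
- BAX 855 naïve, PK-tailored (Protocol 20.2.2.2): the PK infusion is these subjects' first BAX 855 infusion. Vital signs are taken up to 15 minutes before it and at 30 ± 5 minutes after it.
- Transitioning, fixed dose (Protocol 20.2.1.1.1): vital signs are transcribed from the previous study's end-of-study visit, which is the same visit as screening. The post-infusion list then has "Vital signs (body temperature, respiratory rate, pulse rate, and supine systolic and diastolic blood pressure".
- Transitioning, PK-tailored (Protocol 20.2.2.1.1): the same pattern where IR is assessed at screening.

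**Use of baseline.** Change in vital signs is a secondary safety outcome (Protocol 8.4.2.2, SAP 3.1.2.2). SAP 8.4 plans observed and change-from-baseline summaries by age group. SAP 5.9 computes change as the visit value minus the baseline value.

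**The concern.** A safety baseline should be the subject's state before exposure. The same-date clause in SAP 5.5 asks only that the dates match, and the selection is of the last assessment. Where there are readings on both sides of the infusion on one date, the last is the post-infusion one.

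The paired readings around each infusion are there to show acute infusion effects. With a post-dose baseline, the change summary removes the first such effect from Day 1 and puts it, with reversed sign, into later pre-infusion visits. Subjects without a post-infusion reading on Day 1 would keep a pre-dose baseline, so baseline would also mean different things in different subjects.

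**Working it through.** The plan states no figure to reproduce, because the point concerns a derivation rule. The check has three steps.

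**1. Apply the rule to the schedules.** The date rule takes the last non-missing reading dated on or before the reference start date. The comparison rule takes the last reading before the time of the first infusion.

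| First infusion in this study | Vital-sign readings on that date, in order | Baseline, date rule | Baseline, time rule |
|---|---|---|---|
| Naïve, fixed dose, ED1 | pre (within 15 min); post (30 ± 15 min) | post | pre |
| Naïve, PK-tailored, PK infusion | pre (within 15 min); post (30 ± 5 min) | post | pre |
| Transitioning, fixed dose, screening | transcribed end-of-study value; post (30 ± 15 min) | post | transcribed value |
| Transitioning, PK-tailored, screening with IR | transcribed end-of-study value; post (30 ± 15 min) | post | transcribed value |

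The two transitioning rows assume that the infusion at that visit counts as the first in this study. Protocol 10.3.1 also allows it to be part of the previous study's end-of-study IR determination.

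Dropping the same-date clause would not repair the rule. Values dated strictly before Day 1 would give the screening reading for naïve subjects, and none from the coinciding visit for transitioning subjects.

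**2. Effect on change from baseline.** Let v be a subject's stable pre-infusion value and d the acute shift at the first infusion. Assume that nothing else changes.

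| Reading | Value | Change, baseline v + d (date rule) | Change, baseline v (time rule) |
|---|---|---|---|
| Day 1, post-infusion | v + d | (v + d) - (v + d) = 0 | (v + d) - v = d |
| Later visit, pre-infusion | v | v - (v + d) = -d | v - v = 0 |
| Later visit, post-infusion, if the shift recurs | v + d | (v + d) - (v + d) = 0 | (v + d) - v = d |

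Each change is lower by d than it would be against a pre-dose baseline. The last row matters because Protocol 20.2.1.3 and 20.2.2.5 repeat vital signs after the infusion at later visits. A recurring acute effect would there read as no change. The documents give no value or range for d, so the result stays in this form.

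**3. Other planned changes from baseline.**
- SAP 8.2 plans change and shift tables for hematology, clinical chemistry and lipids. Protocol 20.4.2 schedules none of these at ED1, and the schedules list no post-infusion draw for them. For naïve fixed-dose subjects both rules select the screening value.
- SAP 10.5 plans change from baseline for IR, but defines IR from its own pre- and post-dose samples.

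**The case against.** **Intent.** The main sentence of SAP 5.5 speaks of measurements before the reference date, and its paragraph on transitioning subjects tests for a result before first administration. Both suggest that a pre-dose baseline was meant. The same-date clause may exist only to keep a Day 1 pre-infusion value from being lost because its date is not earlier. This is a fair reading, and nothing shows a deliberate choice of a post-dose baseline. But the later paragraph is a fallback and does not restrict the same-date clause. The SAP is explicit where timing matters elsewhere: SAP 8.1 uses the date and/or time of first administration for adverse events, and SAP 10.5 takes the pre-dose FVIII sample for IR. SAP 5.5 has no such condition.

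**Acute effects stay visible elsewhere.** SAP 8.4 also summarises observed values, flags results against fixed age-specific ranges and lists everything. Under Protocol 12.8 the investigator decides whether each abnormal vital sign is an adverse event. None of this uses baseline. Protocol 6.4.2 reports no significant treatment-related vital-sign changes in the Phase 1 study. All of this stands. It limits the consequence to the change summaries and suggests that d may be small, without giving a figure.

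**Output Templates.** These are not among the documents and may separate pre- and post-infusion time points. Separate columns would not by themselves settle which value is baseline.

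**FVIII.** A reader might infer that the same error distorts changes in FVIII level. The rule would indeed label a post-dose FVIII sample as baseline. At 60 IU/kg and the anticipated recovery of 2.5 in Protocol 8.7.3.5, that sample would lie about 60 × 2.5 = 150 IU/dL above the pre-dose value. But no change from baseline in FVIII level is planned: SAP 8.2 does not include it, and SAP 10.5 summarises PK concentrations without it. The inference is not supported.

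**Conclusion.** The point holds for vital signs. Read literally, SAP 5.5 selects the Day 1 post-infusion reading as baseline, and the change summaries in SAP 8.4 would be measured against it. Each change is off by -d for a subject with an acute shift of d at the first infusion. The size of d is unknown from the documents, and the algebra assumes an otherwise stable value.

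The importance is low: one descriptive secondary safety output, with no test attached. The co-primary outcomes (inhibitor development and spontaneous bleeding rate), FVIII level summaries, and hematology, chemistry and lipid changes are not shown to be affected. A reader might also infer that acute infusion effects would go unseen. The documents do not support that, because observed values, range flags and listings do not depend on baseline.

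The conclusion rests on the wording of SAP 5.5 as it stands and on the scheduled post-infusion reading being present. It would fall away if the Output Templates or programming specifications already restrict baseline to pre-infusion readings.

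**What to change.** In SAP 5.5, replace the same-date clause with a rule along these lines:

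- Baseline is the last non-missing value obtained before the date and time of the first BAX 855 infusion in the current study.
- Where the clock time is missing on that date, use the assessment scheduled as pre-infusion, and do not use one scheduled as post-infusion.
- Incremental recovery is exempt. Its baseline is the IR derived from the pre- and post-infusion samples of the baseline IR infusion.

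The exemption is needed. For naïve fixed-dose subjects, baseline IR comes from the ED1 infusion (Protocol 20.3.2, note b). A blanket ban on Day 1 post-infusion values would leave them without a baseline for the IR changes planned in SAP 10.5.

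The cost is a few sentences in the SAP and minor reprogramming. It relies on a pre/post-infusion label or a time being available in the vital signs data. The protocol schedules the readings separately, but neither document states that the vital signs eCRF panels record these fields, so this should be confirmed first.
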